Study population: The study population comprises up to 35 patients with early (≤ 5 years from diagnosis), mild, levodopa-untreated PD. The patients will be on an inhibitor of monoamine oxidase (MAO) that is prescribed for their disease. There is also a pilot study of healthy volunteers (HVs), to measure biological variability of CSF Cys-DA levels.

Design: The study has a one group, pretest-posttest design. Each patient undergoes a lumbar puncture (LP) as an inpatient at the NIH Clinical Center to obtain cerebrospinal fluid (CSF) for assays of Cys-DA, 3,4-dihydroxyphenylacetic acid (DOPAC), and related biochemicals. The second LP is done after the patient has taken at least 5 doses of NAC (2 grams orally twice per day). The LP takes place about 2 hours after the last NAC dose. For the purpose of establishing biological variance and thereby carrying out a meaningful power analysis, we will study up to 6 HVs who undergo 2 LPs as inpatients, with 48 hours between LPs and no NAC treatment. In the study of HVs the main outcome measure is the biological variation of CSF Cys-DA between the 2 LPs.

Outcome measures: The main outcome measure is the CSF concentration of Cys-DA. Other outcome measures are levels of other catecholamine-related neurochemicals or of indices of oxidative stress. Depending on the results, an exploratory study may be done involving NAC at 1 gram orally twice per day. In the pilot study of HVs the main outcome measure is the biological variation of CSF Cys-DA between the 2 LPs.

Table of Contents:

Précis:	3
List of Abbreviations	5
1. Introduction and Background	6
2. Study Objectives	12
3. Subjects	13
4. Study Design and Methods	14
5. Management of Data and Samples	20
6. Additional Considerations	21
7. Risks and Discomforts	22
8. Subject Safety Monitoring	23
9. Outcome Measures	24
10. Statistical Analysis	25
11. Human Subjects Protection	26
12. Anticipated Benefit	27
13. Classification of Risk (for the study as a whole)	28
14. Consent Documents and Process	29
15. Data and Safety Monitoring	30
16. Quality Assurance	31
17. Reporting of Unanticipated Problems, Adverse Events and Protocol Deviations ..	32
18. Alternatives to Participation	33
19. Privacy	34
20. Confidentiality	35
21. Conflict of Interest	36
22. Technology Transfer	37
23. Research and Travel Compensation	37
24. References	38
25. Attachments/ Appendices	41
26. Consent Forms	42

List of Abbreviations

ALDH = aldehyde dehydrogenase

AR = aldehyde/aldose reductase

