Preliminary information: CSF Cys-DA data from 2 patients treated with NAC and 4 HVs who underwent LPs on 2 different occasions under a different protocol are shown in Figure 3. Across the 6 subjects, the correlation coefficient (r value) for the scatter plot relating CSF Cys-DA for the second LP vs. CSF Cys-DA for the first LP was 0.99 (p=0.0002). We predict that in the present study the r value will be even closer to 1 because of the more tightly controlled situation for the 2 LPs. Based on this preliminary information, the reproducibility of CSF Cys-DA is excellent.

[figure not shown]

Figure 3: Scatter plot relating CSF Cys-DA in a second LP to that in a first LP in 2 PD patients (red) and in 4 HVs studied under a different protocol (gray). The linear regression equation for the line of best fit, r value, and p value are shown. Note excellent reproducibility of CSF Cys-DA.

2. Study Objectives

This study is designed to test whether NAC decreases spontaneous oxidation of central neural dopamine in patients with PD.

2.A. Primary objective: The primary objective is to test whether NAC at a dose of 4,000 mg per day decreases CSF Cys-DA levels.

2.B. Secondary objectives: A secondary objective is to evaluate levels of CSF Cys-DA and other catecholamine-related compounds or indices of oxidative stress in CSF or plasma before and after NAC administration. We will also explore whether at a lower dose (2,000 mg per day) NAC produces similar results to those seen with the 4,000 mg per day dose. In a pilot study of HVs we will assess the test-retest variability of CSF Cys-DA.

3. Subjects

3.A. Description of study populations: The study population is patients with PD who are taking an MAO inhibitor for their disease and are not on levodopa. The Planned Enrollment Report for this small study takes into account demographic differences in the prevalence of the disease under study.

The pilot study includes adult HVs.

3.A1. Accrual ceiling: 41.

3.A2. Target number of completers: 10 patients, 6 HVs. Withdrawals/dropouts will be replaced.

3.A3. NIH employees may participate. NIH employees who are subordinates/relatives/co-workers of investigators may not participate.

3.B. Inclusion criteria:

3.B.a. Inclusion criteria for PD Patients

- o PD diagnosed within the past 5 years
- o Taking a monoamine oxidase (MAO) inhibitor
- o Able to provide consent
- o At least 18 years old

3.B.b. Inclusion criteria for Healthy Volunteers

- o Able to provide consent

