7.C. N-Acetylcysteine: NAC is likely safe for most adults, when used as a prescription medication. It can cause gastrointestinal side effects such as nausea or abdominal pain, as well as headache and hypersensitivity reactions. Based on the mechanism of anti-oxidant effects of NAC, no potential drug interactions would be anticipated in PD patients on an MAO inhibitor.

We anticipate that gastrointestinal side effects will be dose-related. If these symptoms occur at the initial dose, they will be considered to be expected non-serious adverse events and reported as such, and the dose will be decreased by one-half. If the symptoms occur at the lower dose, then the NAC will be stopped, the patient will be withdrawn from the study, and the patient will be observed as an inpatient until the symptoms resolve.

Rarely, NAC can cause rashes, fever, headache, drowsiness, low blood pressure, or liver problems. If a patient experiences these symptoms or signs or others that in the opinion of the Principal Investigator are the result of NAC, the patient will be withdrawn from the study.

7.D. Radiation (fluoroscopy): This research study involves exposure to radiation from fluoroscopy if technical difficulty is anticipated or experienced with the lumbar puncture. This radiation exposure is not required for medical care and is for research purposes only. The estimated Effective Dose, **0.05 rem** (2 fluoroscopy procedures), is below the guideline of 5 rem per year allowed for research subjects by the NIH Radiation Safety Committee.

There is no direct evidence that the amount of exposure received from participating in this study is harmful. Pregnancy or lactation are exclusionary in this study.

8. Subject Safety Monitoring

8A. Identify monitors during participation in study procedures: In this study the monitors during participation in study procedures are the Principal Investigator, Research Nurse, or Nurse Practitioner.

8.B. Parameters to be monitored: The parameters to be monitored include symptoms and signs. During all study procedures, subjects are monitored by clinically credentialed personnel of the Clinical Neurocardiology Section (Physician, Registered Nurse, or Nurse Practitioner) or authorized personnel of the NIH Clinical Center (e.g., neuroradiologist).

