8.C. Toxicity criteria to be used: The Protocol requires monitoring of procedures and possible symptomatic side effects of NAC or the development of a post-spinal headache. The NIH's Common Terminology Criteria for Adverse Events (version 4.0) will be used. The patient is queried about any new symptoms at morning rounds on Day 2 and Day 3 during NAC treatment. If the patient reports gastrointestinal side effects at the initial dose, the dose will be halved. All procedures involving more than minimal anticipated risk are administered only by experienced, qualified personnel or personnel.

8.D. Criteria for stopping individual procedures: The PI has the discretion of stopping individual procedures if the medical or psychological risk outweighs the anticipated scientific benefit.

8.E. Criteria for individual subject withdrawal: If a patient develops a post-spinal headache requiring a blood patch, the subject is withdrawn. Subjects may refuse certain tests or procedures, or may withdraw from participation early, without loss of benefits to which they were previously entitled. The Principal Investigator may also exclude a subject from further participation, such as in the event of known or suspect falsification of medical history information or refusal to undergo planned tests or procedures, without loss of benefits to which the subject was previously entitled. If NAC at the initial dose produces gastrointestinal symptoms, the dose will be halved; and if the gastrointestinal symptoms persist after decreasing the NAC dose, then the patient will be withdrawn from the study. If a patient experiences other symptoms that in the opinion of the Principal Investigator are the result of NAC, the patient may be withdrawn from the study. If a woman becomes pregnant while on study, she will be withdrawn.

8.E.1. Withdrawal definition: For record-keeping purposes, "withdrawal" refers to cessation from any further participation in the study, based on the decision of the participant or the Principal Investigator, before the endpoint for participation has been reached. The endpoint for participation is after obtaining CSF while the patient is on N-acetylcysteine. Reaching the study endpoint for participation does not constitute withdrawal.

9. Outcome Measures

In this study outcome is not related to measures of symptoms or signs or a disease but to CSF neurochemical findings.

9.A. Primary outcome measure

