The primary outcome measure is the relative change in CSF Cys-DA levels between pre and post-NAC treatment, which is calculated as: the difference of (CSF Cys-DA at pre-treatment – CSF Cys-DA at post-treatment) divided by CSF Cys-DA at pre-treatment. The change will be dichotomized as decrease vs. no decrease with a threshold decrease to be determined based on the pilot study of HVs.

9.B. Secondary outcome measures

9.B.1. CSF levels of other biochemicals besides Cys-DA. For instance, CSF Cys-DOPA/DOPA ratios may provide an index of oxidative stress in central catecholaminergic neurons.

9.B.2. Percent decrease in CSF Cys-DA expressed as a continuous variable.

9.B.3. In an exploratory study, NAC may be given at 2,000 mg per day.

9.B.4. In a pilot study, reproducibility of CSF Cys-DA will be assessed in a group of HVs studied as inpatients. In this group 2 LPs will be done, separated by 2 days, without NAC treatment prior to either LP. The LPs will be done at about the same time of day, after ingestion of the same pre-determined meal.

10. Statistical Analysis

10.A. Analysis of data/ study outcomes:

For the primary objective, a one-sample t-test (t-test for dependent means) or Wilcoxon signed rank test will be performed to evaluate the difference between pre- and post-NAC treatment for CSF Cys-DA. The proportion of the patients with decreased CSF Cys-DA levels between pre- and post-NAC treatment will be evaluated by the exact binomial test.

For the secondary objectives, one-sample t-tests (t-tests for dependent means) or Wilcoxon signed rank tests will be performed to evaluate the differences between pre- and post-NAC treatment for each secondary outcome.

10.B. Power analysis: Based on the results of the study of HVs, a power analysis will be outlined and approved by the PIRC. The power analysis will be used to justify altering the accrual ceiling for PD patients. The power analysis will be performed using the primary outcome, the difference in CSF Cys-DA between pre- and post-NAC treatment. A one-sample t-test will be applied to estimate the sample size using the standard deviation of the difference calculated from the data in the HVs.

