10.C. Accrual ceiling: Based on power analysis, 10-11 patients with complete datasets would be required to achieve the Primary Objective. Considering the possibility of withdrawals, 15 subjects would undergo inpatient testing. In the exploratory study, up to 20 subjects may be needed to test whether NAC at a 2,000 mg per day decreases CSF Cys-DA levels. Therefore, the accrual ceiling for patients in the study as a whole is 35.

The pilot study about biological variability of CSF Cys-DA levels in HVs will include up to 6 HVs with complete datasets. Dropouts will be replaced.

Therefore, the total accrual ceiling under the protocol is $35 + 6 = 41$ participants.

11. Human Subjects Protection

11.A. Subject selection:

11.A.1. Equitability: Participation in this study is offered to eligible subjects, without regard to race, ethnicity, sex, disability, nationality, religion, handedness, age, or English-language ability. Non-English speakers may be included. In this situation, the short-form consent process will be used.

11.B. Justification for exclusion of children: PD is a disease of middle aged or elderly people.

11.C. Justification for exclusion of other vulnerable subjects: This study does not involve pregnant or lactating women, due to the risks involved. Since this research study involves more than minimal risk without direct benefit, those who are unable to provide informed consent are excluded.

11.D. Justification for sensitive procedures: This study does not involve a placebo, medication withdrawal, provocative testing, or deception.

11.E. Safeguards for vulnerable populations:

11.E.1. NIH staff employee protections: NIH staff and members of their immediate families may participate in this NIH intramural research unless prohibited by the NINDS or excluded by the criteria of the study.

Protections for employees and staff participating in this study include 1) assuring that the participation or refusal to participate will have no effect, either beneficial or adverse, on the subject's employment or position at the NIH, 2) giving employees and staff who are interested in participating the "NIH Information Sheet on Employee Research Participation" prior to obtaining consent, and 3) assuring that there will be no direct solicitation of employees or staff. Independent consent monitoring will be provided by the NIH HSPU.

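### Does section 10.A need a rule for patients whose NAC dose was halved before the primary test of 4,000 mg per day?

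*Combined protocol and SAP*

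**What the plan says.** The objective and the planned schedule name the dose. Section 2.A: "The primary objective is to test whether NAC at a dose of 4,000 mg per day decreases CSF Cys-DA levels". The Précis: "The second LP is done after the patient has taken at least 5 doses of NAC (2 grams orally twice per day"). Section 4.D.4 has a patient on NAC take 2,000 mg shortly before the LP. Section 10.C treats the lower daily dose as a separate exploratory question: "up to 20 subjects may be needed to test whether NAC at a 2,000 mg per day decreases CSF Cys-DA levels".

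The safety sections allow a reduction. If gastrointestinal symptoms occur at the initial dose, 7.C says "they will be considered to be expected non-serious adverse events and reported as such, and the dose will be decreased by one-half". Sections 8.C and 8.E repeat the halving, and 7.C and 8.E withdraw the patient only if symptoms occur or persist at the lower dose. Section 8.E.1, a record-keeping definition, sets no dose condition: "The endpoint for participation is after obtaining CSF while the patient is on N-acetylcysteine".

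The statistics section sets none either. In 10.A the t-test or Wilcoxon test "will be performed to evaluate the difference between pre- and post-NAC treatment for CSF Cys-DA", and "The proportion of the patients with decreased CSF Cys-DA levels between pre- and post-NAC treatment will be evaluated by the exact binomial test". Section 10.C counts data completeness, not dose: "10-11 patients with complete datasets would be required to achieve the Primary Objective".

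**The concern.** Two readings can be drawn. One excludes halved patients, because 2.A asks about 4,000 mg per day and half of that is the exploratory dose. The other includes them, because they are not withdrawn, they reach the endpoint in 8.E.1, and they have complete datasets. With about ten patients, one or two can move a p-value across 0.05, so two analysts could report different answers from the same data. If the set were picked after the Cys-DA results were seen, type I error would rise above 5%. Section 7.C anticipates gastrointestinal effects, so the case is foreseeable. The plan also does not say whether a halved completer counts toward the 10-11 or is replaced; 3.A2 replaces only withdrawals and dropouts.

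**Working it through.** **The plan's own figures.** The accrual sums reproduce: 15 + 20 = 35 patients, and 35 + 6 = 41 participants. The 10-11 completers cannot be reproduced, because no alpha, sidedness, power, SD or effect size is given. Solving backwards with the one-sample t-test (noncentral t, two-sided 0.05, 80% power) gives a standardised effect d = 0.996 at n = 10 and 0.938 at n = 11. I therefore take d = 1.0.

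**Assumed inputs.** n = 10 completers; k = 1, 2 or 3 of them halved; SD of the change = 1; mean change d = 1.0 at full dose and f × d at half dose; two-sided 0.05. The documents give no symptom rate and no half-dose effect, so k and f are varied.

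**How often a halving occurs.** P(at least one of 10) = 1 − (1 − g)^10. For halving rates g = 5, 10 and 20% this is 40, 65 and 89%.

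**Disagreement between the two sets.** For each simulated trial, t = mean / (SD/√n) is computed on all 10 and on the 10 − k full-dose patients. The trial counts as discordant if exactly one result is significant.

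| Half-dose effect f | k=1 | k=2 | k=3 |
|---|---|---|---|
| 0 | 13% | 22% | 29% |
| 0.5 | 10% | 17% | 23% |
| 1 (dose irrelevant) | 9% | 17% | 25% |

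Averaged over a halving rate of 5, 10 or 20% at f = 0.5, discordance is 4.7, 8.8 and 15.7%.

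If halved patients are instead replaced up to 10 at full dose, the comparison is those 10 against the same 10 plus the k halved. At f = 0.5 discordance is then about 8, 11 and 13%.

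**Power by set, without replacement.**

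| Set | k=1 | k=2 | k=3 |
|---|---|---|---|
| Full dose only | 75% | 68% | 60% |
| All completers, f = 0 | 69% | 55% | 42% |
| All completers, f = 0.25 | 72% | 63% | 54% |
| All completers, f = 0.5 | 75% | 70% | 65% |
| All completers, f = 1 | 80% | 80% | 80% |

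The two sets have equal power at f of about 0.40-0.45. With replacement, the full-dose set has 80% power for every k.

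**Type I error.** Either set fixed in advance: 5%. Significant on at least one set, which is the upper bound if the analyst picks afterwards: 6.5, 7.3 and 7.8% for k = 1, 2, 3. Counting only false decreases, the direction of the objective: about 3.3-3.9% against a nominal 2.5%.

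**Exact binomial, null 0.5 (assumed), 2 of 10 halved.**
- Only the two halved patients show no decrease. All: 8/10, 2 × 56/1024 = 0.109. Full dose: 8/8, 2 × 1/256 = 0.008. One-sided: 0.055 and 0.004.
- Only one full-dose patient shows no decrease. All: 9/10, 2 × 11/1024 = 0.021. Full dose: 7/8, 2 × 9/256 = 0.070. One-sided: 0.011 and 0.035, so the conclusion does not change.

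**The case for a change.** The strongest case for a change runs as follows. Section 10.A serves an objective that names a dose, so its silence on dose does not settle membership. The background section justifies a relatively high dose as protection against a false negative, so dose matters to the study's own rationale. Symptoms are asked about on Days 2 and 3, so a halved patient may have taken mixed doses. One or two sentences would close the gap at no cost in patients or procedures.

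Much of this stands. No analysis set is written down, the arithmetic reproduces, and naming the set before results are read would be good practice. The Précis and 4.D.4 also make no provision for the reduction in 7.C, 8.C and 8.E. Those passages must be reconciled, but that is a matter of dosing text and does not bear on the validity of the tests.

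The rest does not carry. The readings are not equally supported: exclusion is inferred from an objective and a planned schedule, while inclusion follows from the wording of the analysis, endpoint and sample-size sections. The discordance is about the same at f = 1 as at f = 0.5, so it largely shows what dropping any two of ten patients does. An analyst who excluded halved patients would naturally still seek 10-11 at full dose, which lowers the discordance. The 15 planned inpatients leave some room for that.

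Nor is there a clearly better set to write in. Power favours all completers above the break-even and the full-dose set below it. Recasting 2.A as a question about a regimen started at 4,000 mg per day would change what a proof-of-concept study asks. The background section does show values from 2 NAC-treated patients, but it does not establish that they belong to this study, so it cannot show that results are already guiding the choice.

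**Conclusion.** No change to the analysis plan follows. This is an unwritten rule about the analysis set that analysts can fill sensibly: analyse every patient with CSF before and on NAC, as 10.A, 8.E.1 and 10.C read, report how many had the dose halved, and show the full-dose patients alongside. The stated tests are valid on either set.

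The stake is at most moderate and rests on assumption throughout. With d = 1.0, two-sided 0.05 and half dose giving half the effect, discordance is about 10/17/23% for 1, 2 or 3 of 10 halved without replacement and about 8/11/13% with it. If no patient is halved, it is nil. The choice between the two sets depends on a half-dose effect that the documents do not give, so neither can be called the correction of an error.

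### Sections 9 and 10 name different primary outcomes, no deciding test is stated, and the 10-11 completers are not justified for the dichotomised outcome in 9.A

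*Combined protocol and SAP*

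**What the plan says.** All references are to the combined protocol and SAP.

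- **9.A** defines the primary outcome as (pre - post)/pre for CSF Cys-DA, and continues: "The change will be dichotomized as decrease vs. no decrease with a threshold decrease to be determined based on the pilot study of HVs".
- **9.B.2** lists as a secondary outcome: "Percent decrease in CSF Cys-DA expressed as a continuous variable".
- **10.A** begins: "For the primary objective, a one-sample t-test (t-test for dependent means) or Wilcoxon signed rank test will be performed". The same paragraph adds: "The proportion of the patients with decreased CSF Cys-DA levels between pre- and post-NAC treatment will be evaluated by the exact binomial test". It gives no order between the two tests and no null proportion.
- **10.B** says: "The power analysis will be performed using the primary outcome, the difference in CSF Cys-DA between pre- and post-NAC treatment", and then: "A one-sample t-test will be applied to estimate the sample size using the standard deviation of the difference", with that standard deviation to come from the healthy volunteers (HVs). The analysis is to be approved by the PIRC.
- **10.C** says: "Based on power analysis, 10-11 patients with complete datasets would be required to achieve the Primary Objective". It names no test and no inputs.
- **3.A2** says: "Target number of completers: 10 patients, 6 HVs".

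The Précis and the primary objective in 2.A speak of the Cys-DA concentration and of whether NAC lowers it. Neither mentions a responder definition.

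**The concern.** The two sections give the primary outcome a different form (binary in 9.A, continuous in 10.B) and a different scale (relative change in 9.A, difference in 10.B). Because 9.B.2 lists the continuous percent decrease as secondary, 9.A cannot simply be read as continuous. Followed as written, the study is sized on one outcome and judged on another.

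Two things are at stake. First, dichotomising a measurement discards information, so a number of completers chosen for a t-test will usually give an exact binomial test less power at the same effect. Second, with both tests listed for the primary objective and no rule between them, the conclusion can depend on which one is taken as decisive after the data are seen. Each completer undergoes two research lumbar punctures, so the number needs a clear basis.

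**Working it through.** **The plan's own figure.** The 10-11 cannot be reproduced, because the documents state no alpha, sidedness, power, effect or SD. Working backwards from a one-sample t-test at 5%, it fits a mean fall, in SDs of the difference, of:

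- 1.00 (n=10) to 0.94 (n=11) for 80% power, two-sided
- 1.16 to 1.09 for 90% power, two-sided
- 0.85 to 0.81 for 80% power, one-sided
- 1.01 to 0.95 for 90% power, one-sided

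**Assumptions for the comparison** (none is in the documents): normal paired differences; the same SD in patients and HVs; mean fall d = 1.0 SD; two-sided 5%; a responder cut-off k of 0, 1 or 1.645 SD, treated as known; binomial null equal to the proportion exceeding k with no treatment effect.

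**t-test.** Power is the probability that a noncentral t variable with n-1 degrees of freedom and noncentrality d√n falls outside the two-sided 5% limits.

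- n=10: noncentrality 3.162, critical value 2.262, power 0.803
- n=11: noncentrality 3.317, critical value 2.228, power 0.848

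**Exact binomial.** p0 = 1 - Φ(k) and p1 = Φ(d - k). Reject if the responder count reaches r, the smallest count with P(X ≥ r | n, p0) ≤ 0.025. Power is P(X ≥ r | n, p1).

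| k (SD) | p0 | p1 | n=10: r, power | n=11: r, power |
|---|---|---|---|---|
| 0 | 0.500 | 0.841 | 9, 0.513 | 10, 0.460 |
| 1 | 0.159 | 0.500 | 5, 0.623 | 5, 0.726 |
| 1.645 | 0.050 | 0.259 | 3, 0.503 | 3, 0.574 |

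So binomial power is 50-62% (n=10) or 46-73% (n=11), against 80% or 85% for the t-test.

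**Starting from the stated number instead of d = 1.0.** If 10 or 11 completers give the t-test exactly 80% power, the same effect gives the binomial test 40-67% (two-sided 5%) or 37-58% (one-sided 5%).

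**Completers for 80% power at d = 1.0.** Exact binomial power is saw-toothed in n, so the figure here is the n from which power stays at 80% or more.

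| | k=0 | k=1 | k=1.645 | Smallest n, t-test |
|---|---|---|---|---|
| 0.025 per tail | 17 | 17 | 25 | 10 |
| One-sided 5% | 16 | 15 | 20 | 8 |

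**Disagreement between the tests** (simulation, n=10, d = 1.0, two-sided; share of all trials).

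| k (SD) | t-test alone significant | Binomial alone significant |
|---|---|---|
| 0 | 29.6% | 0.7% |
| 1 | 22.4% | 4.4% |
| 1.645 | 34.9% | 4.8% |

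At k=1 the binomial is the sole significant test in 4.4/(22.4 + 4.4) = 16% of disagreements. At n=11 and k=1 it is 4.7/(16.8 + 4.7) = 22%.

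**Type I error if either test may count** (two-sided): about 5.2-6.4% across the three cut-offs at n=10 and n=11.

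**The case against.** The strongest reply is that most of the text points to a continuous primary outcome. The Précis, 2.A, the first sentence of 10.A, 10.B and even the opening sentence of 9.A all fit it. Section 10.A also gives the binary outcome its own test, so a reader who infers that the analysis section ignores that outcome would be wrong. What is missing is the order of the tests and a sample size for the binary outcome. This narrows the conflict but does not remove it: the second sentence of 9.A and the listing in 9.B.2 still say otherwise, and no passage reconciles them.

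A reader might also infer that 10-11 is the wrong number for the 9.A outcome. The documents do not show that, because 10.C names no test. Eleven completers would give 91% binomial power for a true proportion of 0.90 against 0.50 at one-sided 5%. It is fair to say only that the t-test is the one sizing method described, so the number is not justified for 9.A.

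It is also true that every power figure above rests on assumed inputs, and that a cut-off taken from up to 6 HVs would not be known exactly. The figures are illustrations. Lastly, 10.B foresees a further power analysis with PIRC approval. That offers a route to resize the study, but it does not settle which outcome is primary.

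**Conclusion.** The plan is wrong as written on this point: it names two different primary outcomes and no deciding test. This follows from the text alone. The stated 10-11 and 10 completers are not justified for the 9.A outcome and cannot be reproduced for either.

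The size of the consequence depends on the assumptions listed in the working. Under them, judging a study of 10 completers by the binomial test instead of the t-test costs roughly 18 to 30 percentage points of power (80% against 50-62%). When the two tests disagree, it is usually, though not always, the t-test alone that is significant.

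Two stronger readings should be set aside. The plan does not carry a large inflation of type I error; the rise is about one percentage point at most to 6.4%. Nor is it a fault in itself to set the responder threshold later from HV data, provided the rule is fixed before patient data are analysed.

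**What to change.** Name one primary outcome on one scale and one deciding test, identically in 9.A, 9.B.2, 10.A and 10.B, before the power analysis goes to the PIRC and before patient data are analysed.

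The simplest route:

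- In 9.A, make the continuous change primary on one stated scale (the relative change is already defined there), and fold 9.B.2 into it.
- In 10.A, name either the t-test or the Wilcoxon test as primary, with the other as a sensitivity analysis.
- Keep the HV-threshold responder proportion as a supportive result with an exact confidence interval.

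If the sponsor prefers to keep the responder outcome as primary, size 10.B and 10.C on the exact binomial test and state the threshold rule and the null proportion.

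In either case, state alpha, sidedness, target power, and the effect and SD on the chosen scale (for a responder outcome, the expected proportion). Then confirm or restate the 10-11 in 10.C and the 10 in 3.A2.

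The cost is text changes and one sample-size calculation, with no new procedures or data items. The outcome not chosen becomes supportive, and the number of completers may change.

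### Section 10.B sizes a t-test on a continuous difference while 9.A's primary outcome is dichotomized, and the 10-11 completers in 10.C have no stated inputs

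*Combined protocol and SAP*

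**What the plan says.** **Outcome.** Section 9.A: "The primary outcome measure is the relative change in CSF Cys-DA levels between pre and post-NAC treatment", computed as (pre − post)/pre. It continues: "The change will be dichotomized as decrease vs. no decrease with a threshold decrease to be determined based on the pilot study of HVs". Section 9.B.2 lists as a secondary outcome: "Percent decrease in CSF Cys-DA expressed as a continuous variable".

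**Analysis.** For the primary objective, section 10.A first names a one-sample t-test or Wilcoxon signed rank test to "evaluate the difference between pre- and post-NAC treatment for CSF Cys-DA". It then adds an exact binomial test of the proportion of patients with a decrease. It does not say which test decides the objective, and it gives no null proportion.

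**Sizing.** Section 10.B: "Based on the results of the study of HVs, a power analysis will be outlined and approved by the PIRC". It goes on: "The power analysis will be performed using the primary outcome, the difference in CSF Cys-DA between pre- and post-NAC treatment". A one-sample t-test is then to be used to "estimate the sample size using the standard deviation of the difference calculated from the data in the HVs".

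**Number.** Section 10.C: "Based on power analysis, 10-11 patients with complete datasets would be required to achieve the Primary Objective". Section 3.A2 sets the target at 10 patients. Section 1 says that the biological variability of CSF Cys-DA is not known and that an estimate is needed before an informed power analysis. Its preliminary data give r = 0.99 between two lumbar punctures in 6 subjects, 2 of them treated with NAC.

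**The concern.** Two things do not fit together.

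First, 10.B and 9.A both use the label of primary outcome, but for different variables. In 9.A it is a yes/no classification of each patient; in 10.B it is a continuous quantity. The continuous version of the relative change is explicitly secondary in 9.B.2. If the plan is followed as written, the calculation that goes to the PIRC will size an analysis other than that of the stated primary outcome. With two unranked tests in 10.A, the deciding one could also be picked once results are known.

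Second, 10.C presents 10-11 as the product of a power analysis, while 10.B describes that analysis as still to come. None of its numerical inputs is reported. A reader cannot tell which NAC effect 10-11 patients were meant to detect, so a null result could not be set against a planned effect.

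**Working it through.** **1. Can 10-11 be reproduced?** A paired t-test calculation needs alpha, sidedness, power, a target mean change and the SD of the change. Section 10.B names the test and the source of the SD, but the documents give a value for none of the five. The correlation of 0.99 does not supply the SD, because SD(difference) = √(s₁² + s₂² − 2·r·s₁·s₂) also needs the two SDs, which the text does not give. Figure 3 is not available and was not used. So 10-11 cannot be reproduced. The accrual sums in 10.C are correct: 15 + 20 = 35 and 35 + 6 = 41.

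**2. What would 10 or 11 detect?** Alpha and power here are assumptions. For n pairs and a standardized change d (mean change divided by its SD), power = P(T > t₁₋α*, n−1), where T is noncentral t with n − 1 df and noncentrality d√n, and α* is 0.025 (two-sided 5%) or 0.05 (one-sided 5%). Solving for d:

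| Sidedness, power | n = 10 | n = 11 |
|---|---|---|
| Two-sided 5%, 80% | 0.996 | 0.938 |
| Two-sided 5%, 90% | 1.155 | 1.087 |
| One-sided 5%, 80% | 0.853 | 0.806 |
| One-sided 5%, 90% | 1.005 | 0.950 |

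So 10-11 fits a t-test for an effect of about 0.8 to 1.2 SD. In the other direction, at two-sided 5% and 80% power, n is 34 for d = 0.5, 15 for 0.8, 10 for 1.0 and 8 for 1.2. The number depends wholly on inputs that are not stated.

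**3. Does the t-test size carry over to 9.A's outcome?** Take n = 10 and d = 0.996, where the two-sided t-test has 80% power. Assume normal changes, a constant shift from NAC, a known SD, and a threshold c (in SDs) that a proportion p₀ of untreated subjects would pass by chance.

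- c = Φ⁻¹(1 − p₀)
- true proportion under NAC: p₁ = 1 − Φ(c − 0.996)
- r = smallest count with P(X ≥ r | 10, p₀) ≤ 0.025
- power = P(X ≥ r | 10, p₁)

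| p₀ | c | r of 10 | attained tail | p₁ | power |
|---|---|---|---|---|---|
| 5% | 1.645 | 3 | 0.0115 | 0.258 | 50% |
| 6.5% | 1.514 | 3 | 0.0233 | 0.302 | 62% |
| 8% | 1.405 | 4 | 0.0058 | 0.341 | 46% |
| 10% | 1.282 | 4 | 0.0128 | 0.388 | 59% |
| 12% | 1.175 | 4 | 0.0239 | 0.429 | 69% |
| 16% | 0.994 | 5 | 0.0130 | 0.501 | 62% |
| 18.5% | 0.896 | 5 | 0.0239 | 0.540 | 72% |

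Power is below 80% in every row. The up-and-down pattern comes from the discreteness of a 10-patient binomial test. Power drops just past each point where r rises by one: at p₀ = 6.7%, for example, 3 of 10 has tail 0.0253, so 4 are needed and power is 37%. The 46% to 72% is therefore the spread over these seven nulls, not a bound.

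**The case against.** The best defence of 10-11 is that 10.B speaks of altering an accrual ceiling, so a ceiling already existed, and that 10.C is worded conditionally. An earlier provisional calculation, to be refined with HV data, is consistent with both. That stands. A reader might infer that no calculation can have been done, and the documents do not support this. They show only that its inputs are not reported and that 10.B and 10.C are not reconciled. The preliminary paired data in section 1 may have informed such a calculation, but in the text they give no SD.

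It is also fair that the t-test in 10.B matches the first test that 10.A lists for the primary objective. Sizing is therefore not detached from the analysis section; the conflict is with 9.A and 9.B.2.

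A reader might further take the difference in 10.A and 10.B to be an absolute one and see a second mismatch with the relative change in 9.A. The wording does not settle this: 10.B calls the quantity the primary outcome, and 9.A has just defined that as relative. The point does not depend on it, because the continuous-versus-dichotomized conflict remains on either reading.

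Finally, the loss of power from dichotomizing depends on the threshold, which is not yet set. The direction holds at every null tried; its size is not established.

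**Conclusion.** The point holds. As written, the planned calculation would size a continuous t-test while the stated primary outcome is dichotomized, and 10-11 completers rests on no reported inputs. If two-sided 5% and 80% power were intended, 10-11 corresponds to detecting about 1.0 to 0.94 SD of the within-patient change. Under the normal, constant-shift assumptions above, the binomial analysis of 10 patients at that effect would have about 46% to 72% power at the nulls tabulated, so the t-test number cannot be borrowed for it.

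It would be tempting to conclude that the trial is underpowered. The documents do not support that: without an SD, a target effect and a threshold, no correct number can be computed, and 10-11 is reasonable for a large standardized effect.

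**What to change.** **(a) One primary analysis.** In 9.A, 10.A and 10.B, name the continuous relative change (pre − post)/pre, tested by the one-sample t-test, as the single primary analysis. Make the dichotomized proportion supportive, so that 9.A and 9.B.2 exchange roles. Take the HV SD on that same relative scale. If the investigators prefer to keep the dichotomized outcome as primary, 10.B should size the exact binomial test, using the HV-derived threshold and the null proportion that goes with it. A null of 0.5 should not be the default; with changes symmetric about zero when there is no effect, it fits only a threshold of zero.

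**(b) State the inputs.** In 10.B give alpha, sidedness, power and the target percentage fall. In 10.C and 3.A2 label 10-11 as provisional until the HV data are in, and restate it as a detectable effect under those inputs. If two-sided 5% and 80% power are chosen, that is about 1.0 SD for 10 completers and 0.94 SD for 11, to be converted to a percentage fall once the HV SD is known.

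**Cost.** Wording in 3.A2, 9.A, 9.B.2, 10.A, 10.B and 10.C, and one short calculation when the HV results arrive. No larger sample and no extra procedures are required. The downside is that the stated adequacy of 10-11 will look less certain and the proportion with a decrease loses its primary status.
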